2.1. Background and rationale

For patients with some acute conditions who present as emergency hospital admissions there is clinical uncertainty as to whether or not they should have emergency surgery. Within the initial emergency hospital admission some patients have emergency surgery (operative care), whereas other patients with similar diagnoses only receive non-operative care which can include medical management or non-surgical procedures (for example, interventional radiology), with some of these patients having surgery deferred to the elective (planned) setting. Complications and readmission rates are higher for emergency than for elective surgery³. Within the emergency general surgery (EGS) specialty, some patients with acute conditions have improved health following emergency surgery and others from non-operative care. However, for many patients the relative benefits, risks and costs of emergency surgery versus non-operative care are unknown. Research is required to evaluate the relative effectiveness and cost-effectiveness of emergency surgery versus non-operative strategies for patients with common acute conditions presenting as emergency hospital admissions to NHS hospitals in England.

In England, although there are approximately 4,000 NHS consultant general surgeons who spend on average 50% of their time on EGS, there is insufficient capacity to provide emergency surgery 24/7⁴. In 2018, there were 697,314 EGS admissions to NHS trusts in England, of which 305,507 (43.8%) did not receive an operative procedure. The Getting it Right First Time (GIRFT) report for EGS, found wide variation across NHS trusts in care quality and outcomes after emergency surgery⁴, which may reflect local logistical and resource constraints, but also clinical uncertainty⁵. For common acute conditions, such as diverticulitis, there are well-developed non-operative strategies and little evidence that emergency surgery leads to better outcomes. Research in the US has reported higher 30-day mortality following emergency surgery versus non-operative care for diverticulitis and some other acute conditions¹.

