Preparatory work to date has utilised emergency admission data for 2014-15 for a sample of half the acute NHS trusts in England. We used ICD-10 diagnosis codes to identify cohorts of emergency admissions, and an initial list of OPCS procedure codes to define relevant surgical procedures for these acute conditions. Table 1 lists the broad acute conditions, intervention and comparator strategies. The TTO estimates from the pilot data highlight that for each of these five acute conditions, there is wide variation in the proportion of patients who have emergency surgery across NHS trust hospitals.

Population

In the proposed study, the populations of interest will be defined by adult patients with an emergency admission to an NHS hospital in England between 1 April 2009 and 30 June 2020 for which one of the five eligible acute conditions is the primary reason for admission. Eligibility will be based on a final list of ICD-10 codes that specify that the acute condition is the 'main' diagnosis, and according to the findings of the first design workshop. For each patient, this admission then forms their *index admission*.

The exemplar, provisional 3-character ICD-10 codes for defining populations comprise: acute and unspecified appendicitis (K35, K37); cholelithiasis (K80); inguinal hernia (K40); diverticular disease of intestine (K57); vascular disorders of the intestine (K55). The final target populations for each condition will be defined with the expert clinical panel, taking place on 29 March 2020, which will determine the specific complications for inclusion related to each pathology.

Our initial analyses will also investigate pathways to diagnosis and to surgical or non-surgical care. This will help the research team and clinical panel refine the criteria for inclusion and exclusion, and for intervention or comparator. We will also examine inconsistencies between diagnoses and procedures and ensure the final definition of acute conditions ensure that for the cohort included they form the main reason for admission. This will involve: examination of diagnosis codes (specific codes and position in all episodes within an emergency admission); source of emergency admission (A&E, GP, inter-hospital transfer, etc); other potential diagnoses, e.g., other abdominal pain (R10); and multiple admissions for the same patient.

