The main potential issues are missing values for case mix variables and failure to record diagnoses, procedures or outcomes. Missing or unreported ethnicity data in eligible admissions (c10%), and deprivation (c1%) will be minimised by using ethnicity and deprivation data from patients' other linked episodes. HES data for age and sex are almost complete. We will recognise the potential impact of improvements in the coding of diagnoses in HES between 2008-2020 by including a covariate for financial year in the analysis models. We will examine the use of diagnosis/procedure codes over time periods to identify other potential issues that need to be considered in defining PICO criteria, for example expanding eligibility to include secondary as well as primary diagnoses. For any missing covariate data, we will make plain any assumptions that we do make, drawing on previous work from ourselves and our collaborators. For example, for baseline covariates with missing values we will examine whether this pattern of missingness differed across the intervention and comparator groups. We will use the approach recommended by Rosenbaum (2010) to making minimal, but transparent assumptions about the missing data while balancing patterns of missingness across intervention and control groups³⁰.

Instrumental variable

Our proposed IV design follows research in pharmaco-epidemiology²⁶ that uses provider preference as an instrument for treatment receipt. In this study, the IV will be the TTO, defined for each acute condition, as the proportion of emergency admissions during which an eligible surgical procedure is undertaken. Hospitals and surgeons will be identified from the HES provider/site of treatment codes, and the consultant/specialty codes as in precedent research by the applicants^{1,30}. In the primary analysis, TTO will be defined at the hospital-level, to recognise that in the NHS, multidisciplinary team input informs the decision to operate. We will also report sensitivity analyses with TTO defined at the trust-level, as in the pilot data, and at the consultant-level, for comparison with the precedent study¹. We will calculate TTO by financial year (2008-09 to partial 2020-21) using HES records for all relevant patients.

Sample size

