We have used a HES data extract which is for 50% of NHS acute hospital trusts for a single financial year (2014-15). We find that this pilot data would provide at least 99% power to detect an absolute risk difference of 10% for all conditions except diverticulitis (57% power). The proposed study will have access to HES data for all NHS trusts for five years, and so we envisage that for each of the five acute conditions, the study will have at least 90% power to detect differences as small as 5% at the 5% level of statistical significance.

Analysis

Checking IV assumptions

For a variable to be a valid instrument for treatment receipt it has to i) predict the receipt of treatment; ii) be independent of baseline covariates; and iii) only affect the outcome indirectly through the treatment²⁵. It is critical to carefully assess these assumptions in an IV analysis. [name] et al. completed a full assessment as to whether TTO met the essential conditions for being an IV in the US context¹. We will carefully assess whether TTO meets the criteria for an IV for each of the five acute conditions described for patients presenting as emergency admissions to NHS hospitals in England.

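### The tendency-to-operate instrument counts each patient's own treatment and is a raw one-year proportion, so chance variation pulls the IV estimate towards the confounded comparison and overstates its precision, most of all for diverticulitis

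*Protocol*

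**What the plan says.** Protocol section 2.2.2, Objective 1, under Instrumental variable, defines TTO for each condition as "the proportion of emergency admissions during which an eligible surgical procedure is undertaken". On the period and the patients counted it says: "We will calculate TTO by financial year (2008-09 to partial 2020-21) using HES records for all relevant patients". On the level: "In the primary analysis, TTO will be defined at the hospital-level", with sensitivity analyses at trust level and "at the consultant-level, for comparison with the precedent study". Nothing in the protocol takes the index patient out of the proportion, pools or lags years, or shrinks small units.

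The pilot used "emergency admission data for 2014-15 for a sample of half the acute NHS trusts in England". From it the protocol concludes that "for each of these five acute conditions, there is wide variation in the proportion of patients who have emergency surgery across NHS trust hospitals". Table 1 gives a diverticulitis trust TTO of 9.0% (IQR 6.6% to 10.9%) and an F statistic of 678. Under Checking IV assumptions, instrument strength is judged by F above 10, to be repeated in the full data at each level of TTO. Under Sample size, the pilot is said to give "at least 99% power to detect an absolute risk difference of 10% for all conditions except diverticulitis (57% power", and five years of all trusts is said to give at least 90% power for a 5-point difference.

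**The concern.** The spread of raw one-year proportions mixes real differences in practice with binomial chance. For a common outcome in large units this matters little. Diverticulitis has a 9% operation rate and fewer than about 210 admissions per trust-year, so the chance part is large.

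What the chance part does depends on whether the index patient is counted. If excluded, the noise is unrelated to that patient's treatment: the instrument is weaker and intervals are wider, but the estimate is not biased by it. If included, as the definition literally reads, the noise contains the patient's own treatment decision. That decision carries the unmeasured severity that the IV design is meant to remove. The instrument then looks stronger than it is, the intervals are too narrow, and the estimate drifts back towards the ordinary treated-versus-untreated comparison.

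**Working it through.** **The plan's own figure.** Pilot power of 57% for 10 points implies effect/SE = 1.960 + 0.176 = 2.136. Half the effect with ten times the data (all trusts, five years) gives 2.136 × 0.5 × √10 = 3.378, and Φ(3.378 − 1.960) = 92%. The stated 90% follows from the 57%. The 57% itself cannot be rebuilt, because no outcome rate or instrument spread is given for it.

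**Noise share, trust level.** Inputs: Table 1 cohorts, taken as nine years; Table 1 medians as p; observed SD = IQR/1.349; an assumed 120 to 160 acute trusts of equal size. Formula: λ = [p(1−p)/m] / (observed SD)², with m admissions per trust-year.

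Diverticulitis: 224,000/9 = 24,889 a year, so m = 207 to 156. Chance SD = √(0.09 × 0.91/m) = 1.99 to 2.29 points. Observed SD = 4.3/1.349 = 3.19 points. λ = 39% to 52%, and 45% at 140 trusts (43-58% if the cohort spans ten years).

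| Condition | λ, 120-160 trusts |
|---|---|
| Diverticulitis | 39-52% |
| Obstruction | 23-30% |
| Hernia | 19-25% |
| Appendicitis | 9-12% |
| Cholecystitis | 4-5% |

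**Hospital level (primary).** With a true SD of 2.36 points (the noise-corrected trust value at 140 trusts) and an assumed 150 to 200 hospitals, m = 166 to 124 and λ = 47-54% for diverticulitis.

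**Consultant level.** The background section says "there are approximately 4,000 NHS consultant general surgeons who spend on average 50% of their time on EGS". 24,889/4,000 = 6.2 diverticulitis admissions and 6.2 × 0.09 = 0.56 operations per consultant-year. The chance of no operation at all is 0.91^6.2 = 0.56. Chance SD is 11.5 points, so λ = 96% if the true SD equals the trust value and about 73% if it is three times that. For the other four conditions λ is 55-91% with equal SD but 12-53% with three times it.

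**Effect on the estimate.** Let τ² be the true variance between units.
- Index patient included: cov(TTO, treatment) = τ² + p(1−p)/m, and cov(TTO, unmeasured severity) = cov(treatment, severity)/m. The fraction of the ordinary least squares (OLS) bias retained is therefore [p(1−p)/m]/[τ² + p(1−p)/m] = λ.
- SE relative to a noise-free TTO: √(1−λ) = 0.74 when included and 1/√(1−λ) = 1.35 when left out, at λ = 0.45. Moving from included to left out therefore multiplies the SE by 1/(1−λ) = 1.82.

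Simulation (140 trusts × 5 years × 178 admissions, true effect 0, unmeasured severity):

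| TTO | Mean estimate | SE | F |
|---|---|---|---|
| Included, annual | 0.008 (OLS 0.020) | 0.015 | 1557 |
| Leave-one-out, annual | −0.002 | 0.028 | 464 |
| Leave-one-out, pooled over the five years | −0.002 | 0.022 | 730 |

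At consultant level (4,000 × 3 years × 6 admissions) the included version gave 0.019 against OLS 0.019, F about 15,000, and 95% intervals covering the truth in 7% of runs. Leave-one-out gave F of 17.

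**Why F > 10 cannot detect it.** With τ² = 0 and the index patient included, the first-stage R² is 1/m, so F ≈ n/m, the number of units. Seventy trusts in one year give F ≈ 70 from chance alone; simulation confirmed 70.

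**What pooling recovers.** For 170 hospitals, with a share s of the true variance stable over three years, c = sτ² + (1−s)τ²/3 and SE ∝ √(c + p(1−p)/(3m))/c. Relative to one-year leave-one-out, the SE falls by 18% (s = 1), 15% (0.9), 11% (0.8) and about 0% (0.6).

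**Power over the full window.** 1 April 2009 to 30 June 2020 is 11.25 years, so effect/SE for 5 points becomes 3.378 × √(11.25/5) = 5.067. With one-year leave-one-out TTO at λ = 0.45:
- if the pilot used a spread net of chance, 5.067 × √0.55 = 3.76, power 96% (94-98% across λ = 0.52 to 0.39);
- if it used the raw spread with the index patient included, 5.067 × 0.55 = 2.79, power 80% (68-87%). Three-year pooling with stable practice brings this to 92% (85-95%).

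**The case against.** Four points deserve weight.

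First, the protocol may leave the exact TTO formula to a later analysis plan, and it schedules published plans. Window length and shrinkage are indeed plan detail. But the protocol does state a construction, a per-year proportion over all relevant patients, and read literally that counts the index patient.

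Second, the trust count is not in the documents. That stands, so the shares are given as ranges.

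Third, at trust level the simulated bias is about half a standard error, and the intervals still covered the truth in 94% of runs. That also stands. The harm there is a shifted estimate with an SE about half what it should be. How far coverage falls depends on the strength of the confounding, which is unknown.

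Fourth, consultant TTO is only a sensitivity analysis, and consultants may vary more than trusts. So chance can be called most of the consultant-level variance with confidence only for diverticulitis.

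Stronger readings are tempting but not supported:
- A reader might infer that the plan as written gives a weak instrument and wide intervals. The sign is the reverse; those follow only once the index patient is excluded.
- A reader might infer that lost precision threatens the study. The documents do not say which spread the 57% used, and the data window is more than twice the five years in the power statement. Full-window power is above 90% on one reading and about 80% on the harshest.
- A reader might infer that variation in diverticulitis is not wide. Net of chance the SD is 2.36 points on 9.0%, a relative spread of about 26%, and the protocol sets no threshold for the word.
- A reader might take the F of 678 as proof of inflation. The Table 1 spread alone would give about 156, but for cholecystitis it would give about 1,850 against a stated 65. The first-stage model is not given, so neither gap proves an error.

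**Conclusion.** The point holds as one of bias and false precision. As defined, the annual TTO includes the patient's own treatment, so the IV estimate keeps a fraction of the confounding bias about equal to the noise share. For diverticulitis that is 39-52% at trust level and about 47-54% at hospital level. It is 4-30% at trust level for the other conditions. The reported SE is close to half of the leave-one-out SE for diverticulitis, and the planned strength check would pass regardless. At consultant level the diverticulitis estimate would be nearly the confounded one, so agreement or disagreement with the US study would mean little.

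This rests on the literal reading of the TTO definition, 120-160 trusts, 150-200 hospitals with the trust-level true SD, units of equal size, and nine cohort years. It should be corrected before analysis, but it does not show that the study cannot answer its question.

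**What to change.** In section 2.2.2, under Instrumental variable:
1. Define the primary hospital TTO as a leave-one-out proportion that excludes the index patient. Recompute the F statistics and the stated power on that TTO, and state which instrument spread the power uses.
2. Alongside the one-year version, report a leave-one-out TTO pooled over the index year and the two preceding years, or a shrinkage estimate. Present it as a way to recover precision, mainly for diverticulitis.
3. For consultant-level TTO, exclude the index patient, pool years, and report reliability before any comparison with the US study.

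No new data are needed. The costs are wider intervals, a pooled TTO that follows real changes in practice less closely, and a shorter window in the first cohort years. The gain from pooling disappears if much of the variation is specific to a year, so leave-one-out is the necessary change and pooling the optional one.

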2.2. Research plan/methods

2.2.1. Methods

Overview

The study will estimate the effectiveness and cost-effectiveness of emergency surgery versus non-operative strategies for common acute conditions that present as emergency admissions to NHS hospitals in England. We will define the target population from emergency admissions within a single data source (HES) to ensure consistent definitions, for example of inclusion criteria, across the patient cohort. The target population will include five acute conditions that present as emergency hospital admissions: appendicitis, cholecystitis, diverticulitis, acute symptomatic hernia, intestinal obstruction. The 'intervention' strategy is defined as emergency surgery within the index hospital episode, and the 'comparator' strategy as non-operative care or 'watchful waiting' within that episode which could include: 'medical management', a 'non-surgical' procedure, and then possibly subsequent planned (elective) surgery.

For each acute condition, the specific definitions of the study population, intervention and comparator will be refined at an early stage of the planned research. The initial definitions of the populations (P), interventions (I) and comparators (C) will be developed with the full HES dataset (phase 1). These initial definitions will be presented to a clinical panel, and then refined through structured discussion. The refined PIC definitions will be applied to the HES dataset, presented to a virtual clinical panel, and finalised (phase 2).

The study will access linked data for emergency hospital admissions from HES and the ONS (data request submitted April 2018; approved 20 September 2018; revised request submitted May 2020; expected data receipt, Sept 2020). We will collate information on diagnosis (ICD-10), case mix, surgical procedures received, resource use and outcomes, including mortality.

Instrumental variable design

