Exclusion criteria for defining the *index admission* will include: age less than 18, a previous emergency admission for the condition within the year prior to the index admission, referrals from tertiary referral centres (see IV assumptions below), and any additional exclusion criteria deemed appropriate by the clinical panel, for example minimum surgical volume thresholds for a particular hospital.

Table 1: Exemplar acute conditions, interventions and comparator strategies, and trust-level tendency to operate (TTO), from pilot HES data (2014-5)

Acute condition ¹	Population ² (estimated cohort 09-18)	Intervention ³	Comparator ³	NHS Trust TTO ⁴ median (IQR)	F statistic ⁵
Appendicitis	333,000	Appendectomy	Supportive care; Antibiotic treatment	89.3% (84.9%, 92.8%)	114
Cholecystitis	422,000	Cholecystectomy	Delayed cholecystectomy	17.3% (11.2%, 25.0%)	65
Diverticulitis	224,000	Resection; Colectomy; Laparoscopic lavage	Antibiotic therapy; intravenous fluid therapy Percutaneous	9.0% (6.6%, 10.9%)	678

			drainage of abscess		
Acute symptomatic hernia ⁶	70,000	Repair of hernia	Watchful waiting; Delayed repair of hernia	46.7% (39.4%, 58.7%)	148
Intestinal obstruction (small or large bowel)	235,000	Adhesiolysis; Colonic stenting; Bowel resection	Watchful waiting with intravenous fluid	29.9% (25.5%, 34.3%)	931

¹Acute condition refers to pathology and ensuing complications. The clinical panel will define specific complications related to pathology for the final inclusion criteria ²Population defined by ICD-10 codes. ³Intervention and elective surgery comparators are defined by OPCS codes. ⁴Percentage of the eligible population with an intervention within index HES episode. ⁵From Cragg-Donald weak identification test. ⁶Includes inguinal hernia, femoral and incisional.

Intervention

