For each acute condition, surgical intervention is defined as an operative procedure corresponding to one of a pre-determined set of OPCS Classification of Interventions and Procedures codes within the index emergency admission. Table 1 includes examples of typical procedures or treatments for each acute condition. Code lists will be refined during the initial phase of the research (see later section for further details). Final criteria for defining a relevant surgical intervention will recognise the timing of surgery with respect to hospital admission, and its relationship with other surgical and non-surgical procedures within the admission. These final criteria will stipulate what delay to surgery is required for it to meet the criteria for a 'comparator' rather than 'an intervention strategy'. Alternative specifications will be considered in sensitivity analyses.

Our preparatory work has identified an extensive list of provisional OPCS procedure codes that indicates the patient has had a surgical intervention. Exemplar procedures include: H01.2 Emergency excision of abnormal appendix (appendicitis); J18.3 Total cholecystectomy (cholecystitis); T20.2 Primary repair of inguinal hernia using insert of prosthetic material (inguinal hernia); H33.5 Rectosigmoidectomy and closure of rectal stump and exteriorisation of bowel (diverticular disease); T41.3 Freeing of adhesions of peritoneum (intestinal obstruction).

Comparator strategy

For each acute condition, the comparator is defined as an eligible admission whose care does not include an operative procedure considered to constitute the intervention. This includes patients receiving non-surgical treatment or diagnostic evaluation as identified by OPCS codes, and those with no procedure recorded during their index admission. The comparator strategies include delayed surgery, defined as having a relevant surgical procedure but after the specified time-frame for the intervention.

Case mix and potential confounders

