In the HES pilot data, we found that the trust-level TTO was strongly associated with receipt of emergency surgery; for each condition the F-statistics exceeded the critical value of 10, and therefore assumption i) was satisfied (see Table 1)³¹. We will repeat these tests of instrument strength for the full HES data for each level of the TTO. For assumption ii) we found that the trust-level TTO balanced the observed covariates, and we will explore this further in the full HES data^{32,33}. Although we cannot assess empirically whether TTO is independent of unmeasured confounders, in the emergency setting this assumption is likely to be justified for hospitals, since the vast majority of patients will attend their local hospital without consideration of the hospital-level TTO. This assumption will be bolstered by the exclusion of patients referred to tertiary referral centres for whom this assumption is less plausible. These patients can be identified from HES data on admission source, and distance to provider. For assumption iii) it seems unlikely that after adjusting for the volume of EGS and the outcomes of previous admissions, that the TTO would have a direct effect on the outcomes. For example, it is unlikely that just because a surgical team prefers to operate, that the patients' outcome would be better (or worse) unless that patient actually underwent an operation. We will use falsification tests to probe the plausibility of assumptions (ii) and (iii). Specifically, we will identify subgroups where all patients receive emergency surgery, and test whether the TTO has an effect on outcomes in these subgroups^{34,35}.

Most IV applications also assume that there are 'no defiers' – patients treated contrary to the physicians' preference^{33,36}. Here, this implies that there are no patients who receive surgery simply because they present in a high TTO hospital and vice versa. Following the approach of Swanson et al. (2015)³⁷ for checking the assumption of 'no defiers', we will survey the clinical panel about their preferences and choice of strategy for a set of hypothetical patients with the above acute conditions using vignette patient profiles. This will allow us to assess the magnitude and direction of any bias due to the presence of no defiers.

Estimation and sensitivity analyses

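### The tertiary-referral exclusion runs in opposite directions in two places, and the provisional ICD-10 list has a vascular code but no entry for intestinal obstruction

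*Protocol*

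**What the plan says.** **Tertiary referrals.** The exclusion criteria for the index admission (Protocol 2.2.2, Objective 1, Population) list "referrals from tertiary referral centres (see IV assumptions below") alongside the age limit and the rule on earlier emergency admissions. The part referred to, Checking IV assumptions, says that independence of the TTO from unmeasured confounders is supported by "the exclusion of patients referred to tertiary referral centres for whom this assumption is less plausible". It adds that these patients can be found from their admission source and their distance from the provider.

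**Condition codes.** The Overview in 2.2.1 names the five conditions: "appendicitis, cholecystitis, diverticulitis, acute symptomatic hernia, intestinal obstruction". Table 1 has the same five. The Intervention subsection gives an exemplar procedure for the fifth, "T41.3 Freeing of adhesions of peritoneum (intestinal obstruction"). The Population subsection introduces its codes with "The exemplar, provisional 3-character ICD-10 codes for defining populations comprise", and the last two entries are "diverticular disease of intestine (K57); vascular disorders of the intestine (K55").

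**The concern.** The tertiary rule is one of the few design supports for an assumption that the protocol admits cannot be checked empirically. If the cohort is built from the exclusion list alone, the patients whom the IV section wants removed stay in the primary analysis, and a different group is removed instead.

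The code list matters because it is the only place in the protocol that ties conditions to ICD-10 categories. Footnote 2 of Table 1 says that the populations there are code-defined, and the preparatory work used ICD-10 codes to form its cohorts. With no obstruction code stated, the obstruction row cannot be traced to a definition. If the vascular entry were carried into extraction, one of the five cohorts would contain a different disease.

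**Working it through.** No power, event-count or error-rate formula bears on this point. The check sets the protocol's statements side by side.

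**1. Direction of the tertiary exclusion**

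- Exclusion criteria: referrals *from* tertiary centres. The patient has left such a centre and arrives at another hospital.
- Checking IV assumptions: patients referred *to* tertiary centres. The tertiary centre is the receiving hospital.
- The two sets may overlap, for example in a transfer between two tertiary centres, but neither contains the other.
- Rationale: independence is called likely because most emergency patients go to their nearest hospital whatever its TTO. A patient sent on to a specialist centre breaks that reasoning, which fits *to*.
- Identification: distance to the provider describes how far the patient is from the receiving hospital, which also fits *to*. Admission source could serve either direction, so it does not decide the matter.
- Status: the criterion is stated as one that the exclusions will include. It is not marked provisional. The panel may add criteria.

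**2. Conditions against codes**

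| Condition (2.2.1 Overview and Table 1) | Entry in the provisional ICD-10 list | Condition attached to the exemplar procedure | Match |
|---|---|---|---|
| Appendicitis | Appendicitis, K35 and K37 | Appendicitis | Yes |
| Cholecystitis | Cholelithiasis, K80 | Cholecystitis | Related; label differs |
| Diverticulitis | Diverticular disease, K57 | Diverticular disease | Related |
| Acute symptomatic hernia | Inguinal hernia, K40 | Inguinal hernia | Partial: Table 1 footnote 6 also covers femoral and incisional |
| Intestinal obstruction | None | Intestinal obstruction | No |
| None | Vascular disorders, K55 | None | No |

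Four conditions have a related entry. Obstruction has none, and the K55 entry matches no condition or procedure in the protocol. No code book is needed, because the protocol's own label for K55 shows the mismatch.

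**3. What can be sized**

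- Table 1 cohorts, in thousands: 333 + 422 + 224 + 70 + 235 = 1,284. The obstruction row is 235 / 1,284 = 18.3% of the total. That is the size of the row whose code is unstated. It does not count misclassified patients.
- A bias from retained tertiary referrals would be roughly (difference in mean outcome that they cause between high- and low-TTO hospitals) / (difference in surgery rate between those hospitals). The protocol gives no share of such referrals, no outcome for them and no relation to TTO, so the numerator is unknown.
- The denominator is not settled either. Table 1 gives trust-level interquartile widths from 10.9 − 6.6 = 4.3 points (diverticulitis) to 58.7 − 39.4 = 19.3 points (hernia), a 19.3 / 4.3 = 4.5-fold range. The primary TTO is at hospital level.

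**The case against.** The strongest reply concerns the code list. It is expressly an example, and it does not decide eligibility: "Eligibility will be based on a final list of ICD-10 codes that specify that the acute condition is the 'main' diagnosis". Settling populations by code is the first of the panel's three tasks: "The final target populations for each condition will be defined with the expert clinical panel, taking place on 29 March 2020". The protocol also undertakes to look for mismatches between diagnoses and procedures, and that check should expose a vascular diagnosis paired with adhesiolysis. The definitions shown to the panel are to be developed from the full HES data, so the protocol does not say that this list goes to the panel unchanged. All of this stands, and it limits the consequence. It does not make the entry right, because an example has to be an example of one of the five conditions.

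A reader might infer that the panel reviewed and kept K55, since the protocol already reports a data request of May 2020. The documents do not support this. The Population subsection still treats the March 2020 panel as a future event, so that text may simply not have been updated.

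On the tertiary rule, the exclusion criterion sends the reader to the IV section, and anyone who follows the cross-reference meets the other wording. That makes an error less likely, but it leaves two incompatible instructions, and the firm list of criteria is the one that appears to be out of line.

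The hernia mismatch is weak. K40 is one entry in an exemplar list, and footnote 6 of Table 1 already states the wider scope.

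**Conclusion.** Both mismatches are real and can be checked within the protocol. The tertiary conflict carries more weight, because it sits in a criterion not marked provisional and bears on instrument independence. The cross-reference, the rationale and the distance criterion all favour *to*, but the intended direction is for the sponsor to confirm. The obstruction entry is an error in a provisional list. The hernia codes are a minor alignment.

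Three stronger readings are not supported:

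- **One of the five cohorts will be the wrong disease.** Final codes are deferred to the panel, so this is a risk only.
- **The Table 1 obstruction figures are for vascular disease.** The row's label and procedures indicate obstruction, and the protocol does not say which codes produced it.
- **The retained tertiary patients bias mortality by a stated amount, or chose their hospital because of severity.** Any figure would need an invented referral share, excess mortality and gradient across TTO. The protocol says only that independence is less plausible for these patients and does not mention severity.

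The point calls for a correction before extraction. It does not show that the design fails.

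**What to change.** 1. Once the sponsor has confirmed the direction, reword the exclusion criterion to remove patients referred to tertiary referral centres, identified as Checking IV assumptions describes, so that both places carry one rule. If the other direction was meant, the IV section needs changing and its rationale restating.
2. Replace the vascular-disorders entry with the ICD-10 category for intestinal obstruction. The sponsor should supply the code, since the protocol does not give it.
3. State which codes produced the Table 1 obstruction row. Re-run its cohort size, TTO and F statistic only if K55 was used.
4. Align the hernia codes with footnote 6 of Table 1, or say that the inguinal code is only an example.

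The cost is a few lines of text and one query to whoever ran the pilot extraction, plus at most one pilot row to repeat. All of it should be done before the cohorts are extracted.
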